3.0 STUDY OBJECTIVES

3.1 Primary Objectives

- a) Develop new quantitative metrics of baseline SC uptake on SPECT/CT imaging and correlate with clinical parameters of liver function and clinical outcomes in liver cancer patients receiving RT or surgery.
 - Hypothesis: Global metrics of baseline pre-treatment SC uptake on SPECT/CT imaging are more predictive for survival than conventional clinical measures of liver function and are associated with ICG clearance. For patients receiving surgery, the volume of the future liver remnant (FLR) as defined by SC SPECT/CT imaging (functional FLR) is more predictive for PHLF than CT-defined FLR volumes. Heterogeneity metrics of baseline SC uptake are associated with the severity of cirrhosis and prior liver-directed therapy; specifically, SC uptake within the liver is more heterogeneous in less compensated livers and in those that have received a higher number of liver-directed therapies.
- b) Correlate *post-treatment* changes in SC uptake on SPECT/CT imaging with changes clinical liver function.

Hypothesis: Changes in SC uptake between pre-RT and mid-RT/post-RT SPECT/CT scans are associated with changes in clinical liver function in response to RT and are predictive of liver toxicity at earlier time points compared to clinical assessments of liver function. SC uptake in the FLR (non-treated) is stable and preserved over time between pre-surgery and immediately post-surgery (3-5 days postoperative) scans.

Secondary Objectives

- a) Estimate the dose response relationship on multiple spatial scales (global liver, regional liver, liver image voxel) between radiation dose and changes in SC uptake, both acutely (mid-RT) and subacutely (1 month post-RT), using SC SPECT/CT imaging.
 - Hypothesis: Deficits in SC uptake due to absorbed dose is governed by a linear dose relationship. As the dose delivered to the region/voxel increases, the uptake in SC decreases in a linear fashion.
- b) Estimate the degree of radiation response in liver tissue with varying levels of function (i.e. compare radiation dose response of well compensated livers against less compensated livers).

This may establish a threshold of liver tissue that would be "safe" to treat without significantly affecting liver function.

Hypothesis: Varying degrees of cirrhosis have different radiation dose response curves; specifically, more cirrhotic livers have a lower threshold for injury (more radiosensitive) than less cirrhotic or non-cirrhotic livers. The dose-response relationship can be modeled either as a linear or sigmoid function.

c) Correlate SC uptake on SPECT/CT imaging in FLR with extent of liver hypertrophy after surgical resection.

Hypothesis: In patients undergoing surgery, the functional FLR is predictive of the adequacy of the FLR and the extent of liver hypertrophy after hepatectomy. Higher functional FLR decreases the risk of PHLF and has a higher capacity and ability to hypertrophy compared to less functional FLR.

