As a validation step, these baseline SC imaging data will be correlated to indocyanine green (ICG) clearance in patients (in those who opt to undergo this study), which assesses liver function based on the rate of clearance of a contrast agent over serial blood draws, and is considered a standard assessment of global liver function. ICG is a water-soluble compound that is selectively taken up by hepatocytes and transported into the biliary system without undergoing metabolism [37]. ICG clearance, therefore, can be utilized as an index of functioning hepatocyte mass [38] and is correlated with prediction of liver dysfunction and mortality associated with surgical resection [39]. The retention rate of ICG 15 minutes after administration (ICG-R15), a ratio of the ICG concentration at 15 minutes to its initial concentration in the blood, will be used to benchmark SC uptake metrics against. Higher ICG-R15 rates indicate worse liver function and would be expected to be correlated with lower global SC uptake metrics.

Functional FLR will be generated by calculating the volume of liver within the optimal image threshold as defined above. Anatomic FLR will be delineated and calculated on CT or MRI images using portal and hepatic veins as landmarks for segmental division. Logistic regression analyses and Pearson chi-square test will be used to compare the ability to predict for PHLR between functional FLR and anatomic FLR.

b) Correlate *post-treatment* changes in SC uptake on SPECT/CT imaging with changes clinical liver function. Relative changes in the parameters identified at baseline will be tested for correlation to changes in clinical liver function, including CTP score and ALBI grade, as well as their individual constituents.

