4.2.1 Primary Endpoints

a) Significant differences in Wilcoxon rank sum of ROC-optimized SC SPECT parameters will be tested between CTP classes. Spearman rank correlations between optimal SC SPECT parameters and clinical liver function parameters will be tabulated for the following categories: (1) composite liver function scoring systems (CTP score, ALBI grade), (2) individual quantitative liver function components (albumin, bilirubin, INR), and (3) individual qualitative clinical liver function components (encephalopathy, portal hypertension, ascites, and splenomegaly). Qualitative components will be treated as binary categorical variables (yes/no). Imaging and clinical parameters of liver function will be tested for association with overall survival. Continuous variables will be dichotomized above and below a threshold value that maximized accuracy of classification under ROC with balanced sensitivity and specificity. Univariate Cox proportional hazard regression will then be performed on all continuous and categorical variables. Statistically significant variables will serve as inputs into multivariate Cox proportional hazard regression. A stepwise backwards variable selection procedure will be followed to remove non-significant variables with high cross-correlation until the model log-likelihood is maximized.

Because radiomics generates feature sets of ~50 metrics, machine learning methods will be utilized to develop predictive models that are robust against overfitting, utilizing feature selection and classification/regression methods such as support vector machines, Bayesian analysis, and decision trees. These machine learning methods will be compared against standard statistical methods, such as ROC analysis and Kaplan-Meier estimation / Cox regression, for association to clinical liver function, prior liver-directed therapies, clinical outcomes (i.e. survival), and toxicity (i.e. CTP score progression).

b) The same set of statistical analysis will be performed for association of post-treatment changes in SC uptake on SPECT/CT imaging to clinical endpoints. Machine learning methods will test whether post-treatment changes in SC SPECT/CT provide independently predictive information after adjusting for baseline parameters.

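### The clause that SC change predicts liver toxicity earlier than clinical assessment has no planned analysis that can test lead time

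*Combined protocol and SAP*

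**What the plan says.** Section 3.1, objective (b), sets out to correlate post-treatment changes in "SC uptake on SPECT/CT imaging with changes clinical liver function". For the RT cohort its hypothesis has two clauses. The first is that SC changes are associated with changes in clinical liver function. The second is that they "are predictive of liver toxicity at earlier time points compared to clinical assessments of liver function".

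The analysis text for (b) is short:

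- Section 4.1.1(b): "Relative changes in the parameters identified at baseline will be tested for correlation to changes in clinical liver function, including CTP score and ALBI grade".
- Section 4.2.1(b): "The same set of statistical analysis will be performed for association of post-treatment changes in SC uptake on SPECT/CT imaging to clinical endpoints".
- Section 4.2.1(b), next sentence: "Machine learning methods will test whether post-treatment changes in SC SPECT/CT provide independently predictive information after adjusting for baseline parameters".

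The set of methods carried over from 4.2.1(a) contains rank tests, Spearman correlations, ROC analysis, Cox regression and machine learning. Its outcomes include "clinical outcomes (i.e. survival), and toxicity (i.e. CTP score progression". For survival, "Imaging and clinical parameters of liver function will be tested for association with overall survival", and significant variables of both kinds enter one multivariate Cox model.

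On timing, Section 4.0 gives Cohort A (n = 40) a baseline scan, a mid-RT scan and a scan about 1 month after RT. The Table 1 footnotes place the serum liver tests within 2 days of each scan. Table 1 schedules a physical exam and history for Cohort A at screening and at 1 month, but not at mid-RT. Section 7.0 adds a review of clinical records at 6 months.

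**The concern.** A claim of earlier prediction needs three things: an event that happens after the predictor is measured, a rival clinical predictor measured at the same early time, and a comparison of the two. The plan states none of them for toxicity. CTP progression has no date or window, so a CTP rise already present at mid-RT could count both as the clinical assessment and as the event that SC is meant to foresee. Adjustment for baseline parameters does not remove what the mid-RT laboratory tests already show.

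At stake is the reading of a primary hypothesis. Early imaging is useful for adapting treatment only if it tells the clinician something that same-visit blood tests do not. A significant association between SC change and clinical change could be taken as support for the whole sentence in objective (b), although it bears only on the first clause.

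**Working it through.** The plan gives no alpha, power, effect size or expected correlation for this objective, so there is no figure to reproduce.

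**Step 1. Match each planned analysis to the clause.**

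| Planned analysis | Toxicity dated after the scan? | Compared with clinical change at the same visit? |
|---|---|---|
| Correlation of SC change with CTP, ALBI and components (4.1.1(b)) | Not stated | No; clinical change is the outcome |
| Association with CTP progression (4.2.1) | Not stated | Not stated |
| Association with survival, joint Cox model (4.2.1) | Survival is later, but is not liver toxicity | Not stated |
| Machine-learning test of independent prediction (4.2.1(b)) | Not stated | No; adjusted for baseline only |

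No row meets both conditions.

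**Step 2. How often would the association be positive with zero lead?** Inputs: n = 40 (Section 4.0); two-sided 5% level (assumed); true correlation r between SC change and clinical change of 0.3, 0.4 or 0.5 (assumed). Spearman test, 2,000 simulated trials per value: 42.4%, 69.1% and 89.0% significant.

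Closed-form check: ρ = (6/π)·arcsin(r/2), standard error of atanh(ρ) = √(1.06/37) = 0.169, power ≈ Φ(atanh(ρ)/0.169 − 1.96).

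- r = 0.3: ρ = 0.288, atanh = 0.296, ratio 1.75, power about 42%.
- r = 0.4: ρ = 0.385, atanh = 0.405, ratio 2.40, power about 67%.
- r = 0.5: ρ = 0.483, atanh = 0.526, ratio 3.11, power about 88%.

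The two agree within about 2 percentage points. All 40 patients are assumed to have complete pairs.

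**Step 3. Does the association separate lead from no lead?** A second simulation (1,500 trials per scenario, n = 40) made SC change and clinical change equally good noisy readings of one underlying liver change, at mid-RT and at 1 month. Assumed: reliability 0.5 or 0.7; correlation between mid-RT and 1-month underlying change 0 or 0.6; toxicity 10%, 20% or 40%, defined as clinical worsening at 1 month. The direct test was a DeLong comparison of the AUCs of the two mid-RT changes.

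- *No lead.* The same-visit association was significant in about 87–90% of trials at reliability 0.5 and over 99% at 0.7. The two mid-RT AUCs agreed within 0.01. The direct test rejected in about 4–7% at 20–40% toxicity, and in 8–11% at 10% toxicity (4 events), where DeLong is anti-conservative.
- *True lead* (mid-RT clinical change is pure noise; correlation 0.6). The 1-month association was significant in about 87–89% at reliability 0.5 and over 99% at 0.7, essentially as with no lead. The direct test rejected in only about 19–34%, with a standard error of the AUC difference of about 0.13–0.20.

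So the 1-month association is equally positive whether or not SC leads.

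**Step 4. Events available.** Section 2.0 quotes RILD in 5–67% of patients: 0.05 × 40 = 2 and 0.67 × 40 = 26.8, or about 2 to 27 events. The figure is for RILD, not CTP progression, so it is only a rough guide.

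**The case against.** The strongest defence is that the text is open on timing. Neither section says that changes are paired at the same visit. Survival necessarily follows the scan, imaging and clinical variables meet in one Cox model, and machine learning is to test independent prediction. An analyst could use mid-RT SC change to predict later CTP progression without departing from the plan. This stands. A reader might infer that the plan offers only a same-time correlation, or no joint model of imaging and clinical measures. The documents do not support either reading.

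Two other stronger readings also fail. The 42–89% might be taken as a false-positive rate for objective (b). It is not, because in every such scenario the association clause is true and a significant test is correct for it. And the clinical comparator might be thought identical to the outcome. CTP is listed in both roles, but ALBI, albumin, bilirubin and INR are also named as clinical measures, so the overlap is partial and arises mainly because the event is undated.

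It is also fair to say that this is a pilot, that the objective itself says only *correlate*, and that no text promises to report a correlation as earlier prediction. None of this supplies an analysis for the timing clause, which stands as a hypothesis under a primary objective.

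**Conclusion.** The point holds in this form: the earlier-than-clinical clause has no stated analysis that can test it. Toxicity is undated, and the independent-prediction test adjusts for baseline parameters but not for clinical change at the same visit. That rests on the text alone.

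The size is illustrative. Significance in 42–89% of trials with zero lead depends on assumed correlations of 0.3–0.5 and complete data; at 0.3 it is under half. The reliabilities, path correlations and toxicity rates in the second simulation are also assumptions. The conclusion that association cannot reveal lead does not depend on their exact values.

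The claim that SC would be falsely declared an earlier predictor goes beyond the documents; the risk is of over-reading. This should be corrected before analysis. It does not affect the association clause or the other objectives.

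**What to change.** In Section 4.2.1(b), add for Cohort A:

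1. **Outcome.** For this clause, toxicity is CTP progression from baseline first recorded after the mid-RT visit, using the 1-month visit and the 6-month record review.
2. **Landmark set.** Exclude patients with progression already evident at mid-RT. Because Table 1 schedules no mid-RT exam, a full CTP score is not a scheduled item. State that this is judged from the mid-RT laboratory values (bilirubin, albumin, INR) plus any ascites or encephalopathy recorded in the chart.
3. **Comparison.** Use mid-RT relative change in TLF as the predictor and compare it with mid-RT change in ALBI score from same-visit laboratory tests. Also report SC change adjusted for that ALBI change.
4. **Reporting.** Give the paired AUC difference with a bootstrap confidence interval, labelled as an estimate and not a powered test.

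Alternatively, remove the timing claim from the hypothesis and keep the association clause.

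Cost: no new scans, blood draws or visits. It does need a written landmark rule and extraction of CTP components from charts at mid-RT and 6 months, where no CTP assessment is specified. Excluding early progressors reduces the events further. The interval will be wide, and power is low (about 19–34% in the scenarios above) even if SC truly leads.

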1.0 INTRODUCTION

Title	Functional Liver Imaging with Sulfur Colloid SPECT/CT in Primary and Metastatic Liver Cancer Patients Receiving Liver-Directed Treatment: A Pilot Study
Short Title	Sulfur Colloid SPECT/CT for Liver Cancers
Phase	Pilot Study
Methodology	Single Arm Open-Label
Study Duration	4 years
Study Center(s)	University of Washington Medical Center
Objectives	Study the use of SPECT/CT imaging with ^{99m} Tc sulfur colloid to characterize functional liver in patients receiving liver-directed treatments for liver cancers, and characterize liver tissue response to these treatments. The long-term goal is to use functional liver imaging to personalize liver-directed therapies in liver cancer patients by improving risk stratification and reduce treatment-related hepatotoxicity.
Number of Subjects	60 evaluable subjects
Diagnosis and Main Inclusion Criteria	Patients diagnosed with primary (hepatocellular carcinoma, cholangiocarcinoma) and metastatic liver cancers receiving liver-directed therapies (external beam radiation therapy, surgery).
Study Product, Dose, Route, Regimen	99mTc sulfur colloid SPECT/CT scans
Duration of administration	Drug administration will consist of 3 SPECT/CT scans with ^{99m} Tc sulfur colloid (one baseline scan which is standard of care, two follow-up scans which are experimental and paid for by departmental research funds).
Statistical Methodology	^{99m} Tc sulfur colloid SPECT/CT parameters will be extracted, selected, and tested for statistical association to clinical liver function status and post-treatment toxicity using a variety of statistical methodologies. Receiver-operator characteristic (ROC) analysis will determine the optimal operating point for liver function classification accuracy using SC SPECT/CT parameters. Hypothesis testing of differences between independent groups will proceed using non-parametric Wilcoxon ranksum between 2 groups or Kruskal-Wallis ANOVA between >2 groups. Hypothesis testing of differences between imaging time points of the same subjects will proceed using non-parametric Wilcoxon sign-rank or Friedman ANOVA paired comparison. Survival analysis will consist of Kaplan-Meier estimation, log rank testing, and Cox proportional hazard regression. Dose-response models will be constructed from linear and logistic regression. Prediction models will utilize robust feature selection and feature fitting through multi-fold cross validation as part of a general machine learning framework.

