4.0 STUDY DESIGN

General Design

This is a pilot study of utilizing SPECT/CT imaging with 99m Tc-SC to accurately identify and quantitate functional liver tissue on serial imaging in patients receiving RT or surgery for liver cancer. The long-term goals are to use functional imaging to improve risk stratification for selecting which patients should undergo aggressive local treatments with RT or surgery and to aid in RT planning by preferentially sparing functional liver tissue, thereby leading to reduced liver toxicity. There will be two cohorts of patients: those receiving RT (Cohort A) and those undergoing surgery (Cohort B). A total of 60 patients will be enrolled (Cohort A, n = 40; Cohort B, n = 20).

All patients will have a total of 3 SPECT/CT imaging with ^{99m}Tc-SC. The first scan in both cohorts will be routine medical care (not experimental) and will take place prior to initiation of RT or surgery. Two follow up scans will be part of the protocol. In cohort A, the first follow up scan will occur at mid-RT, and the second one about 1 month post-RT (prior to any potential anatomical liver changes). In cohort B, the first follow-up scan will occur 3-5 days postoperatively (prior to any potential liver hypertrophy), and the second one about 1 month post-operatively (when liver hypertrophy is expected to occur).

Endpoints

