4.1.1 Primary Endpoints

a) In this study, patients with liver cancer will undergo SPECT/CT imaging with ^{99m}Tc-SC at the time of RT planning for cohort A and within 1-2 weeks prior to surgery for cohort B. All image datasets will be imported into MIM 6.0, and fused with the RT planning CT and radiation plan for cohort A and with the contrast-enhanced diagnostic CT or MRI scan.

To characterize whole-organ liver function, all pre-treatment SPECT/CT images will be analyzed for 1) ratios of maximum, mean, and total liver SC uptake relative to spleen SC uptake (L/S) and 2) volumetric SC parameters such as the functional liver volume (FLV) formed by 58% maximum image intensity threshold segmentation. Optimal image thresholds for SC SPECT parameter association to CTP classification (A vs. B/C class) will be interrogated by receiver-operator characteristic (ROC) analysis. Image thresholds that yield maximum AUC in quantitative parameters such as FLV ratio, L/S ratio, and their total liver function (TLF) product will be propagated to the remaining analyses. In cohort A receiving RT, planned dose-volume and dose-function metrics within the tumor-subtracted liver and functional liver volume(s) will

feature mean dose, $D_{xx\%}$ (the dose given to xx% of liver volume), V_{zz} (the liver volume which receives zz Gy), and fV_{zz} (the percentage of total liver function which receives zz Gy).

To characterize spatial distribution of functional liver, radiomics will be applied to SC SPECT/CT images via a locally-developed open source radiomics toolkit [33]. In addition to the whole-organ SC SPECT/CT metrics descried above, radiomic features will include intensity histogram features, along with a variety of textural features derived from co-occurrence matrices, neighborhood difference matrices, and zone size matrices [34-36].

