7.0 TREATMENT PLAN

All patients will receive radiation or surgical treatment per standard of care. As part of this study, all patients will undergo three SC SPECT/CT scans (**Fig. 1**):

First scan will prior to the start of treatment. This scan will be standard of care clinically for
patients undergoing liver-directed therapy and will be at the time of radiation treatment planning
in the treatment position for the RT patients (Cohort A) or within 2 weeks prior to surgical
intervention for surgery patients (Cohort B).

- 2) Second scan will be mid-radiation treatment in Cohort A, to assess the acute response of functional liver to radiation. For patients treated with a 5 fraction regimen, this mid-treatment scan will occur after the 3rd fraction (+/- 2 days acceptable) and after the 8th fraction for patients treated with a 15 fraction regimen (+/- 2 days acceptable). For Cohort B, this scan will be within 3-5 days post-surgery to assess for the functional stability of the liver remnant.
- 3) Third scan will assess the longer term response of functional liver tissue to treatments. In Cohort A, this will be 1 month post-radiation (up to 2 months is acceptable). In Cohort B, this will be 1 month +/- 2 to 6 weeks post-surgery.

Follow-up of all patients will occur via standard clinical follow-up procedures by the treating physician. This clinical follow-up will include clinical exam, standard serum liver function tests and tumor markers, and CT or MRI scans for continued cancer surveillance and treatment response. Research staff will review clinical records at 6 months post-treatment. See Table 1 below for summary.

Table 1. Study Calendar.

Cohort A (Radiation Therapy Patients)

	Screening	Prior to Start of Radiation Treatment	Mid-Radiation Treatment	1-Month Post- Radiation Treatment
Informed Consent	X*			
Physical Exam	X			X
Medical History	X			X
Standard Serum Liver Function and Tumor		X	X	X
Marker Tests†**				

Serum Pregnancy Test††	X			
defail Fregulaticy rest				
ICG Clearance Test		X*	X*	X*
(optional)†				
CT or MRI scan	X			Χ
99mTc-SC SPECT/CT scan		Χ¶	X*	X*

^{*}Denotes a research procedure; all others are standard of care.

Cohort B (Surgery Patients)

Concrete (Cargory Fationts)	Screening	Prior to Surgery	3-5 Days Post- Surgery (inpatient)	1 Month Post- Surgery +/- 2 to 6 weeks (outpatient)
Informed Consent	X*			
Physical Exam	X			X
Medical History	X			X
Standard Serum Liver		Х	X	X
Function and Tumor Marker Tests†**				

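### Primary objective (b) expects remnant uptake to be unchanged after surgery, but the only planned comparison of scans within patients tests for a difference and so cannot confirm that

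*Combined protocol and SAP*

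**What the plan says.** Section 3.1, primary objective (b), states the cohort B hypothesis that "SC uptake in the FLR (non-treated) is stable and preserved over time between pre-surgery and immediately post-surgery (3-5 days postoperative) scans". Section 7.0 gives the early postoperative scan the same purpose: "For Cohort B, this scan will be within 3-5 days post-surgery to assess for the functional stability of the liver remnant".

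The methods that could bear on this are:

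- **Synopsis (section 1.0), Statistical Methodology:** "Hypothesis testing of differences between imaging time points of the same subjects will proceed using non-parametric Wilcoxon sign-rank", with Friedman as the alternative.
- **Section 4.1.1(b):** "Relative changes in the parameters identified at baseline will be tested for correlation to changes in clinical liver function".
- **Section 4.2.1(b):** "The same set of statistical analysis will be performed for association of post-treatment changes in SC uptake on SPECT/CT imaging to clinical endpoints". The plan adds machine learning to see whether changes predict outcome beyond baseline.

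Two kinds of metric are defined, both in section 4.1.1(a). The first is whole-organ: "To characterize whole-organ liver function, all pre-treatment SPECT/CT images will be analyzed for 1) ratios of maximum, mean, and total liver SC uptake", with the spleen as the reference, together with functional liver volume and the product of the two. The second is the functional future liver remnant (FLR), which is a volume: "Functional FLR will be generated by calculating the volume of liver within the optimal image threshold as defined above". Neither is assigned to the comparison of the pre-surgery and 3-5 day scans.

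On size, section 4.0 says: "A total of 60 patients will be enrolled (Cohort A, n = 40; Cohort B, n = 20"). The documents give no alpha, SD of change, margin or sample-size derivation for this comparison.

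**The concern.** Stability is a claim that any change is small enough not to matter. A test whose null hypothesis is no change can count against that claim. Failing to reject the null says only that the data did not show a change, and that outcome becomes more likely as pairs are lost or measurements get noisier. The analyses under (b) answer a different question: uptake could fall in every patient and still correlate, or fail to correlate, with clinical liver function.

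The plan therefore states an expectation under a primary objective without saying how it would be judged. At stake is whether the report can say anything defensible about early preservation of remnant function. The scan itself has other uses (the change correlations, and a reference point before hypertrophy), so its value does not depend on this comparison alone.

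The metric is a second gap. A whole-liver volume or total falls after resection because tissue has been removed, and the functional FLR is a volume, not an uptake. An uptake measure confined to the remnant has yet to be specified.

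**Working it through.** The logical point needs no arithmetic. The figures show how weak a non-significant result would be as evidence. The plan has no figure of its own to reproduce.

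**Inputs.** From the documents: at most 20 pairs (section 4.0). Assumed: two-sided 5% for the difference test, normally distributed paired changes, and effects in units of the SD of the paired change, because no SD is given. A case with 16 pairs (4 lost) is also assumed. Section 7.0 foresees withdrawals but gives no rate, and the synopsis calls the 60 subjects evaluable where section 4.0 calls them enrolled, so losses might be replaced.

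**Step 1: power of the signed-rank test.** The exact critical values are W ≤ 52 for 20 pairs (level 4.84%) and W ≤ 29 for 16 pairs (level 4.43%). Simulation with 100,000 trials per case gives:

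| Pairs | Power at 0.5 SD | Non-significant at 0.5 SD | Change with 80% power |
|---|---|---|---|
| 20 | 54% | 100 − 54 = 46% | about 0.68 SD |
| 16 | 43% | 100 − 43 = 57% | about 0.78 SD |

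**Step 2: what an interval would show.** The half-width of a t-interval is t × SD / √n.

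- 20 pairs, 95%: 2.093 / √20 = 0.468 SD. 90%: 1.729 / √20 = 0.387 SD.
- 16 pairs, 95%: 2.131 / √16 = 0.533 SD. 90%: 1.753 / √16 = 0.438 SD.

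Unlike a p-value, the interval shows directly which sizes of change the data exclude.

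**Step 3: could 20 pairs support a formal claim?** The rule tested is that the 90% t-interval lies wholly inside ± a margin.

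- 20 pairs, no true change: 39% power at a margin of 0.5 SD and 80% at 0.68 SD.
- 20 pairs, true shift of 0.2 SD: power at the 0.68 SD margin falls to about 65%.
- 16 pairs, no true change: 80% power needs a margin of about 0.77 SD.
- 20 pairs, one-sided reading (no important loss, one-sided 5%, no true change): a margin of about 0.58 SD gives about 80% power.

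In percentage terms, the smallest margin with 80% power for 20 pairs and no true change is 0.68 × SD. An assumed SD of change of 10, 15, 20 or 30 points gives margins of about 7, 10, 14 or 20 points. These SDs are illustrations, not estimates.

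**The case against.** The strongest reply is that objective (b) is mainly about correlating changes with clinical liver function, which the plan does analyse. The stability sentence is one expectation for one cohort in a single-arm pilot. The difference test can refute it, and a small observed change would be descriptive support. Much of this stands. It would be too strong to say that no result could count in the hypothesis's favour: what is missing is a rule for confirming it and a stated estimate with its precision.

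A reader might also infer that the investigators intend to read a non-significant test as stability. The documents do not say so; they leave open how the hypothesis would be judged. The risk is that the plan does nothing to prevent that reading.

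A third reply is that a formal equivalence rule is too much for a pilot. This stands in part. The Background (section 2.0, Clinical Data to Date) says such changes have not been studied in liver resection, so a margin may be hard to defend. For that reason estimation is the default remedy below and equivalence is conditional.

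Two opposite inferences about cohort size should also be resisted: that 20 pairs are too few for an equivalence claim, or that they are enough. Either depends on an SD and a margin that the documents do not give.

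**Conclusion.** The concern holds in this form: the plan states a no-change hypothesis under a primary objective, names only a difference test for comparing time points within patients, and gives no interval, margin or remnant-restricted uptake metric by which stability could be assessed. This follows from the text alone and does not depend on the calculations.

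Its size, under the stated assumptions, is that even with all 20 pairs a true fall of half an SD would be missed nearly half the time. Non-significance would be weak evidence of stability. The gap should be closed, but the remedy is modest and the pilot's design does not need to change.

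**What to change.** In section 4.2.1(b), for cohort B:

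1. Specify one uptake metric restricted to the remnant, for example the liver-to-spleen mean uptake ratio of section 4.1.1 applied to the FLR contour. Measure it in the same remnant on the first and second scans, using the contrast CT that section 7.0 already schedules with each scan.
2. Report its paired relative change with a confidence interval (Hodges-Lehmann, in keeping with the plan's non-parametric approach, or a t-interval) and the number of complete pairs.
3. State that a non-significant difference will not be read as stability.
4. Reword the hypothesis as estimation of the change. Only if the investigators can justify a margin before analysis, conclude that uptake is stable when the 90% interval lies within it. If a one-sided reading is intended, conclude that uptake is preserved when the lower bound excludes a loss of that size.

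The cost is a few sentences, with no extra patients, scans or data. The downside is that a stability claim becomes harder to make and this part of the objective may end as estimation only, which is acceptable in a pilot.
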